7.1 Overall trial design

Overview

This is a randomised, double-blind, placebo-controlled, parallel-group, multi-centre, phase 3 clinical trial in adult subjects with severe AD ineligible to treatment with CSA. The trial will consist of a screening period, a treatment period, and a safety follow-up period. The primary endpoint is assessed at Week 16, and the final efficacy assessment will be conducted at Week 26.

A schematic of the trial design is provided in [Panel 1](#).

Screening period (Week -6 to Week 0)

The screening period has a minimum duration of 2 weeks and a planned maximum duration of 6 weeks. The exact duration of the screening period for the individual subject depends on the length of any washout period needed (as also specified in the exclusion criteria in [Section 8.3](#)):

- 6 weeks for subjects using tanning beds or phototherapy.
- 4 weeks for subjects using systemic immunosuppressive/immunomodulating drugs, systemic corticosteroid use, or ≥ 3 bleach baths during any week within the 4 weeks.
- 2 weeks for subjects using topical PDE-4 inhibitors.

If no washout or a 2-week washout period is required, screening will be reduced to 2 weeks and reduced to 1 visit (Week -2; visit 2), i.e., the 2 planned screening visits will be merged. Eligibility will be assessed at the (first) screening visit and on Day 0 (hereinafter “baseline”) prior to randomisation.

All subjects will attend a screening visit 14 days before baseline (Week -2; visit 2) where they will receive electronic diary (eDiary) training and start completion of the electronic patient-reported outcome (ePRO) questionnaires in the eDiary. Data entered into the eDiary during the 2 weeks before randomisation will be used to calculate baseline values of the patient-reported outcomes (PROs).

All subjects will use an emollient twice daily (or more, as needed) for at least 14 days before randomisation and will continue this treatment throughout the trial (including safety follow-up). Subjects will initiate emollient treatment no later than the Week -2 visit. On lesional skin,

emollients should only be applied at a time where TCS is not applied; on TCS-untreated areas, the emollients may be applied at all times.

Treatment period (Week 0 to Week 26)

Following the screening period, approximately 250 subjects will be randomised 1:1 to one of the following groups stratified by prior CSA use (yes/no), country (Germany: yes/no), and baseline disease severity (IGA 3 or 4):

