3. From the date of permanent discontinuation of IMP due to the COVID-19 pandemic.

The date of this event will be the date of the administration of rescue treatment.

- **Prolonged interruption of IMP dosing due to the COVID-19 pandemic:**

A temporary pause in dosing due to the COVID-19 pandemic may influence the interpretation of the subsequent outcome for the subject, and the event will therefore be reported.

At the first occurrence, for which a subject misses IMP doses in one of the 4 following scenarios, the subject will be defined as having a prolonged interruption of IMP due to the COVID-19 pandemic:

1. 3 consecutive missed IMP doses, for which at least one of them is due to the COVID-19 pandemic.
2. 2 consecutive missed IMP doses, for which at least one of them is due to the COVID-19 pandemic and the third consecutive IMP dose is delayed for more than 7 days beyond the planned date of the IMP dosing.
3. Week 22 and Week 24 IMP doses and the Week 26 visit are missed, for which at least one of them is due to the COVID-19 pandemic.
4. Week 22 and Week 24 IMP doses are missed, for which at least one of them is due to the COVID-19 pandemic, and the Week 26 visit is delayed for more than 7 days beyond the planned date.

In scenarios 1 and 3, the start date of the event will be the planned date of the third consecutive missed IMP dose or the Week 26 visit. In scenarios 2 and 4, the start date of the event will be the planned date of the third consecutive IMP dose +7 days or the Week 26 visit + 7 days.

- **Missing data due to the COVID-19 pandemic:**

The collection of data at planned visits allows to report if data is missing due to the COVID-19 pandemic, either due to the subject being prohibited from visiting the sites or the visit being performed via telephone/video, thereby only allowing for a subset of data to be collected.

In the context of some of the efficacy analyses, data recorded missing due to the COVID-19 pandemic will be handled differently from data missing for other reasons. As an example, it may not be reasonable to impute missing binary responder values as a non-response if the missingness is due to the COVID-19 pandemic.

It should be noted that a subject may have missing data due to the COVID-19 pandemic, even though the subject may not have discontinued IMP permanently or temporarily due

to the COVID-19 pandemic. This could e.g. be the case if the subject continue treatment with tralokinumab via home-use ([Appendix 8](#)).

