14.3.8.1 Primary estimand: ‘COVID-19 modified composite’

The primary estimand for the primary endpoint will be:

- Treatment difference in response rates of EASI75 after 16 weeks achieved without rescue treatment and treatment discontinuation, as if the COVID-19 pandemic did not happen

The primary estimand assesses the expected difference in response rates (defined as response obtained without initiation of any rescue treatment and/or permanent discontinuation of IMP) after 16 weeks, resulting from initiation of a treatment regimen with tralokinumab+TCS compared to a treatment regimen with placebo+TCS.

Primary analysis for the primary estimand

Subjects who prior to the Week 16 visit have received rescue treatment or permanently discontinued IMP, without subject-onset of the COVID-19 pandemic, will be considered non-responders at all visits after the relevant event occurs ([Panel 13](#)).

The non-responder imputation reflects an assumption that such initiation of rescue treatment and permanent discontinuation of IMP indicates failure of the randomised treatment to achieve response. Furthermore, this reflects that a (possible) observed positive response after initiation of rescue treatment or permanent discontinuation of IMP is not attributable to the randomised treatment.

Any missing or collected data from subjects who have subject-onset of the COVID-19 pandemic as their first prior intercurrent event will not be used, but instead imputed assuming missing at random (MAR) following the start of subject-onset of the COVID-19 pandemic.

Data missing prior to any intercurrent event will be handled as non-response, unless data is missing due to the COVID-19 pandemic, in which case it will be imputed assuming MAR.

The procedure for imputing values according to the rules described will be implemented in a 2-step procedure, where all missing or ignored data (irrespective of reason) initially will be imputed using MAR based on available data from all subjects. The non-responder imputation of data not affected by the COVID-19 pandemic will be handled subsequently.

The initial MAR imputation will be implemented using the same multiple stepwise imputation method as specified in Section 14.3.8.4 for the primary analysis of the hypothetical binary estimand. The multiple imputation (MI) procedure sequentially builds 100 complete data sets by stepwise use of an ANCOVA model from Week 2 to Week 16 assuming MAR within treatment groups.

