### **6.5 Rescue treatment**

Presentation of rescue treatment and the definition of rescue treatment is as defined in the protocol.

For the presentation of rescue treatment up until the Week 16 visit (actual or nominal) the planned date of the Week 16 visit will be used if no Week 16 visit exists (actual or nominal).

Due to the allowance of TCS in the screening period, some subjects might during this period use TCS of a high enough potency to be categorised as rescue treatment ending on the day of randomisation. Such cases will not be categorised as rescue medication as the assumption will be that the use of high potency TCS will stop prior to administration of IMP.

The global start date of the COVID-19 pandemic is defined in Section [6.8.2](#).

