### 6.8.6 Timing of intercurrent events

Actions taken based on intercurrent events will be dependent on whether or not an intercurrent event happens prior to a relevant visit. The rule will be that if any regarded intercurrent event happens prior to the date of the visit then the intercurrent event will be defined to be prior to the relevant visit. The following list of dates will be used in a prioritised manner as the date of the visit, i.e. if a date higher in the hierarchy exists that date will be used:

1. Observed date of the visit. When no data is available from the scheduled visit, data and visit date can be mapped to the visit per the rules stated in Section 6.8.4.
2. Planned date of the visit – 7 days, to account for the visit window.

In case intercurrent events occurs on the same date the following prioritise list will be used: rescue treatment, permanent discontinuation of IMP, and then subject-onset of the COVID-19 pandemic.

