### 6.8.7 Rules for single imputation methods

Worst observation carried forward (WOCF) will be defined using the worst observation ever recorded between the baseline visit and the analysed visit (baseline assessment included). The date of the analysed visit will be defined as the observed date of the visit if existing, if not then the date of the planned visit + 7 days, i.e. the last assessment before or within the window for mapping an early termination visit or unscheduled visit to a planned visit.

The LOCF value will be used in some cases but only when data is missing and is defined as the last assessment obtained before the observed date of the visit if existing, if not then the planned date of the visit + 7 days.

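### SAP 6.8.6 dates an unheld visit 7 days early: rescue 7 to 4 days before a COVID-missed visit is imputed instead of counted as failure, and interruption scenario 3 cannot act at Week 26

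*SAP*

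**What the plan says.** SAP 6.8.6 treats an intercurrent event as preceding a visit "if any regarded intercurrent event happens prior to the date of the visit". The visit date comes from a two-item list. Item 1 is the observed date, or the date of an early termination or unscheduled visit mapped under SAP 6.8.4. Item 2 covers visits with neither: "Planned date of the visit – 7 days, to account for the visit window".

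Three protocol rules meet this one:

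- **14.3.8.1, primary analysis.** Subjects with rescue or permanent discontinuation before Week 16, without subject-onset of the pandemic, "will be considered non-responders at all visits after the relevant event occurs". A value missing with no earlier event is also non-response, unless it is missing because of COVID-19. It is then multiply imputed (MI) under missing at random.
- **14.3.1, rescue.** For a visit not conducted because of COVID-19, rescue is attributed to the pandemic from 3 days before the planned date.
- **14.3.1, prolonged interruption.** Scenario 3 applies when "Week 22 and Week 24 IMP doses and the Week 26 visit are missed", at least one of them for COVID-19. Scenarios 1 and 3 share one dating rule: "the start date of the event will be the planned date of the third consecutive missed IMP dose or the Week 26 visit". Prolonged interruption is one of the components of subject-onset (14.3.7), for which Panel 13 prescribes MI.

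SAP 6.6.1 and 6.8.5 say that intercurrent events are handled as in the protocol.

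**The concern.** Moving an unheld visit back by 7 days shortens the period in which an event counts as earlier than the visit. An event that falls in the gap is treated as if it had not happened.

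For rescue, the subject drops to the row for no prior event with data missing due to COVID-19, and a treatment failure can be imputed as a responder on the primary endpoint. For scenario 3 the error runs the other way: a value that should be imputed can become a failure at Week 26. Both concern how a value is classified in the primary estimand, which should be settled before the code is broken.

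**Working it through.** No figure in the plan is at issue, so the check is to apply the date rules.

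**Inputs.** Planned days are 7 × 16 = 112 and 7 × 26 = 182 (SAP Table 8). The fallback dates are 112 − 7 = 105 and 182 − 7 = 175. The protocol visit window is ±3 days (Panel 2), so Week 16 opens on day 109. COVID-19 attribution of rescue also starts on day 112 − 3 = 109. The mapping window is −6 to +7 days (SAP 6.8.4).

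**(a) Rescue before a Week 16 visit missed for COVID-19.** Assume no mapped visit, the previous dose given and no earlier event.

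| Rescue first started | Day | Prior under 6.8.6 (day < 105)? | COVID-attributed (day ≥ 109)? | Value under SAP | Value with planned date (day < 112) |
|---|---|---|---|---|---|
| −8 | 104 | yes | no | non-response | non-response |
| −7 to −4 | 105–108 | no | no | **MI** | **non-response** |
| −3 to −1 | 109–111 | no | yes | MI | MI (subject-onset) |
| 0 | 112 | no | yes | MI | MI |

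Only the four days −7 to −4 change. They lie before the protocol's own visit window and before COVID-19 attribution starts. At Week 26 the same band is days 175–178. If the visit was missed for another reason, the value is non-response under either date.

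The stated reason for the 7 days does not quite fit either. Mapping opens on day 106, so an event on day 105 precedes every visit that could be mapped to Week 16, yet 105 < 105 is false. By Table 8, day 105 is the last day of the Week 14 window (7 × 14 − 6 = 92 to 7 × 14 + 7 = 105).

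**(b) Scenario 3 at an unheld, unmapped Week 26 visit.** The event is dated on day 182. The test 182 < 175 is false. With the planned date and a strict test, 182 < 182 is also false, so moving the date alone does not cure this part.

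- Scenario 4 has the same two missed doses, but Week 26 is held more than 7 days late. It is dated 182 + 7 = 189 and the visit falls on day 190 or later; 189 < 190 is true, so scenario 4 acts.
- Protocol 7.1 says "the final efficacy assessment will be conducted at Week 26", so scenario 3 has no later efficacy visit at which to act.
- If the unheld visit carries a COVID-19 reference, MI applies by either route. If it does not, the SAP gives non-response where Panel 13 gives MI.
- If the Week 20 dose was also missed and at least one of the three doses was missed for COVID-19, scenario 1 is met on day 7 × 24 = 168. Since 168 < 175, subject-onset already acts. Part (b) therefore concerns subjects outside that group.

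**Size per subject.** There are 250 / 2 = 125 subjects per arm, with design EASI75 rates of 40% and 15% (protocol 14.1). Taking the design rate as the imputed chance of response, one switch between MI and non-response moves the arm by:

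- tralokinumab: 0.40 / 125 = 0.32 points, so 1 / 0.32 ≈ 3 subjects per point
- placebo: 0.15 / 125 = 0.12 points, so 1 / 0.12 ≈ 8 subjects per point

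An assumed 1 to 10 subjects in one arm gives 0.32 to 3.2 points, or 0.12 to 1.2 points.

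**The case against.** **The protocol does not date an unheld visit.** SAP 6.8.6 fills a gap and gives a reason for its choice. That is fair as to form. But the choice leaves days −7 to −4 uncovered although they precede any visit in the protocol window, and protocol 14.3.8.1 treats rescue there as failure.

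**The cases are narrow.** This stands. Telephone and video visits have a recorded date (Appendix 8, section 3) and fall under item 1. Protocol 9.5 asks for EASI and IGA just before rescue, and an unscheduled visit for that purpose from day −6 onward would be mapped. If IMP was already unavailable because of COVID-19, the rescue is COVID-attributed and MI is correct. For (b), sites are told to give COVID-19 as the reason when no contact is made. A subject recorded as having discontinued permanently would usually be dated well before day 175 (SAP 6.8.2).

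**Other analyses give cover.** Partly. The composite estimand gives non-response in both cases. The tipping-point analysis shifts only COVID-related imputed values in the tralokinumab arm. It does not reach the placebo arm or the non-response in (b), and SAP 6.6.3.1 drops it for IGA 0/1.

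**Scenario 3 may be for reporting only.** Protocol 14.3.1 does say that the event will be reported. But 14.3.7 makes it part of an intercurrent event that governs the analysis, and scenario 4 acts at Week 26. The intent remains an inference.

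Three stronger readings are tempting, and the documents do not support them:

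- *Scenario 1 fails in the same way at Week 16.* Protocol 11.1 places dosing last at a visit, so a dose missed at Week 16 cannot affect the Week 16 assessment. A visit held on or before day 112 would not count that onset either.
- *The SAP contradicts itself by dating one unheld visit on days 105, 112 and 119.* The dates serve different ends: event timing (6.8.6), a descriptive rescue table (6.5), and how late a value may be carried forward (6.8.7, "if not then the date of the planned visit + 7 days").
- *Pruritus diary weeks are misclassified too.* The SAP does not say that the fallback date governs diary weeks, so this rests on a reading that it does not state.

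**Conclusion.** The point holds in two narrow forms, both in the primary estimand for site-assessed binary endpoints (such as EASI75 and IGA 0/1) at visits with no observed or mapped date. Part (a) follows directly from the text: four rescue onset days give MI where the protocol gives non-response. Part (b) also follows as date logic; that scenario 3 was meant to act at Week 26 is inferred from scenario 4 and from Week 26 being the last efficacy visit.

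The effect is small. The documents do not give the number of subjects, and the per-subject shifts of about 0.32 and 0.12 points assume imputed response at the Week 16 EASI75 design rates. No design rates are given for IGA 0/1 or Week 26, so for those the figures are only a yardstick. Against a planned difference of 40 − 15 = 25 points, nothing here suggests that the trial's conclusion is at risk. It should still be corrected, because a stated rule that can turn a treatment failure into a possible responder on the primary endpoint is wrong as written, and the change is cheap.

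**What to change.** In SAP 6.8.6, item 2, replace the planned date minus 7 days with the planned date, as SAP 6.5 already does for the rescue table, and keep the strict test. This repairs (a) and leaves rescue on the planned day itself as not prior, in line with the same-day rule in protocol 14.3.5. Add one line: subject-onset by prolonged-interruption scenario 3 counts as prior to the unheld Week 26 visit. Held and mapped visits stay under item 1.

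The cost is two lines and a re-derivation of the event flags. A permanent discontinuation not due to COVID-19, dated on days −7 to −1 before an unheld visit, also becomes prior. At a COVID-missed visit it then gives non-response in the primary estimand, as 14.3.8.1 states. A few subjects may also move between the discontinued and not-discontinued imputation groups of the treatment policy estimand. If the code has already been broken, report the number of subjects in (a) and (b) by arm, with the re-derived result, in the clinical trial report.

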### 6.8.7 Rules for single imputation methods

Worst observation carried forward (WOCF) will be defined using the worst observation ever recorded between the baseline visit and the analysed visit (baseline assessment included). The date of the analysed visit will be defined as the observed date of the visit if existing, if not then the date of the planned visit + 7 days, i.e. the last assessment before or within the window for mapping an early termination visit or unscheduled visit to a planned visit.

The LOCF value will be used in some cases but only when data is missing and is defined as the last assessment obtained before the observed date of the visit if existing, if not then the planned date of the visit + 7 days.

### 6.8.8 Technical aspects of attributing events and missing data to the COVID-19 pandemic

#### Definition of identifying interference by the COVID-19 pandemic in comment fields/logs

In addendum 1, it was introduced that to attribute events to the COVID-19 pandemic the eCRF comments fields/log had to be used to identify when trial related procedures were interrupted due to the COVID-19 pandemic by writing “COVID-19”. However, alternative ways of specifying this should be accounted for and therefore if any comment fields/logs contain one of the following search terms it will be treated as equal to writing “COVID-19”:

Trial ID: LP0162-1346	Date: 21-OCT-2020	Version: v1.0 Page 33 of 35
-----------------------	-------------------	--------------------------------

“COVID” and “CORONA”. Note, this will capture cases where there is written "CORONAVIRUS", as this would be included by the "CORONA" search term. All comments will be used in an uppercase format.

#### Permanent discontinuation of IMP due to the COVID-19 pandemic

Permanent discontinuation of IMP will be attributed to the COVID-19 pandemic if reason for permanent discontinuation of IMP contains a COVID-19 reference.

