	
 • A helminth parasitic infection within 6 months prior to the date informed consent is obtained. • Tuberculosis requiring treatment within the 12 months prior to screening. • Known primary immunodeficiency disorder.
Investigational medicinal products	
Tralokinumab
 
 • Tralokinumab is a human recombinant monoclonal antibody of the immunoglobulin G4 (IgG4) subclass that specifically binds to human interleukin (IL) 13 and blocks interaction with the IL-13 receptors. • Active substance: tralokinumab. • Dosage form: solution (in accessorised pre-filled syringe, 1.0 mL fill volume). • Concentration: 150 mg/mL. • Dose: 300 mg every 2 weeks (Q2W) following an initial loading dose of 600 mg • Method of administration: Subcutaneous (SC). 
Placebo
 
 • Placebo contains the same excipients in the same concentration only lacking tralokinumab.
Auxiliary medicinal product (AxMP)	
TCS (Europe: Class 3 [potent])
 
Mometasone furoate, 0.1% cream provided in kit sizes of 180–225 g every 2 weeks.

Duration of treatment	
Each subject's trial participation will be up to 46 weeks, divided into a screening period (including washout, if applicable) of up to 6 weeks, a treatment period of 26 weeks, and a follow-up period of 14 weeks.
 
Eligible subjects may be invited to enter a long-term extension trial conducted under a separate protocol (LP0162-1337, ECZTEND). Subjects who transfer to ECZTEND must have had their last visit in the treatment period (Week 26 under the current protocol).

Number of subjects	A total of 250 subjects will be randomised 1:1 to treatment with tralokinumab 300 mg+TCS or placebo+TCS.
Number and distribution of trial sites	Up to 40 clinical sites in Europe are anticipated. Distribution between countries will be based on feasibility. Inclusion of subjects from Germany is prioritised.

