14.1 Sample size

With a significance level of 5%, a sample size of 250 subjects will provide 99% power for detecting a treatment difference for the primary endpoint, assuming an EASI75 response rate at Week 16 of 40% vs 15% for tralokinumab+TCS and placebo+TCS, respectively. Assuming a response rate of 30% vs 15% in reduction of Worst Daily Pruritus NRS (weekly average) score of at least 4 from baseline to Week 16 for tralokinumab+TCS and placebo+TCS, respectively, the trial will provide at least 80% power for rejecting the hypotheses related to the primary endpoint and the secondary endpoint evaluating pruritus at Week 16.

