- **Infection with COVID-19:**

Infection with COVID-19 as an AE may give rise to one of the scenarios described above but will not be handled differently from other types of AEs.

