14.3.16 General principles

Unless otherwise stated, all significance tests will be 2-sided using the 5% significance level. All CIs will be presented with 95% degree of confidence. An observed-cases approach will be used for tabulations of data by visit (i.e. involving only those subjects who attended each specific visit).

Categorical data will be summarised using the number and percentage of subjects in each category and treatment group. Continuous data will be summarised using the mean, median, standard deviation, 1st quartile, 3rd quartile, minimum, and maximum values.

All the analyses specified in the protocol will be reviewed in relation to the blinded data actually obtained and the statistical analysis plan and the analysis set definition document will be finalised before breaking the randomisation code.

Any changes from the statistical analysis planned in this clinical trial protocol will be described and justified in a protocol amendment, the statistical analysis plan, and/or in the CTR dependent on the type of deviation.

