5.2 Injections of tralokinumab

Prior to self-injection at home, the subject will receive proper training in SC injection technique and on procedures to be followed in case of an emergency during or following home-use of tralokinumab. Tralokinumab will be injected by the subject when AE assessments have been completed.

All IMP self-injections need to be documented in the eCRF with 'COVID-19' written in the comments log for the visit in scope.

Subjects who misses one or more doses need to be documented in the eCRF with 'COVID-19' written in the comments log for each visit in scope.

Further details on IMP-injection are provided in the Trial Product Handling Manual. Subjects will also receive a pamphlet with instructions for IMP home-use and a Log of Drug Administration.

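### Pandemic attribution rests on a literal match for `COVID` or `CORONA` with no documented check of the matches, and a match can move a subject from non-response to MAR imputation in the primary estimand

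*SAP*

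**What the plan says.** SAP 6.8.8 puts comment text in upper case. If a comment field or log "contain one of the following search terms it will be treated as equal to writing" the COVID-19 label, the pandemic is taken as the cause. The terms are `COVID` and `CORONA`. The test is then applied to four items:

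- **Permanent discontinuation:** "Permanent discontinuation of IMP will be attributed to the COVID-19 pandemic if reason for permanent discontinuation of IMP contains a COVID-19 reference".
- **Missed visit:** a match in the comments log for that visit.
- **Missed dose:** a missed visit so attributed, or a match in the dosing comment.
- **Missing assessment:** a missed visit so attributed, a match in the log of an attended visit (read as a telephone or video contact), or a match in the comment for the assessment.

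Protocol 10.3 requires a free-text specification when the discontinuation reason is 'AE' or 'other'. Under protocol 14.3.7, 14.3.8.1 and Panel 13, a discontinuation attributed to the pandemic is subject-onset and is imputed under MAR in the primary estimand; any other discontinuation is non-response. Data missing with no prior intercurrent event divide in the same way.

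Protocol 14.3.1 grounds the special handling in an external circumstance and says causality is documented in the eCRF. Its one sentence on COVID-19 infection as an AE allows that infection may lead to one of the pandemic scenarios, "but will not be handled differently from other types of AEs".

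Protocol Appendix 8, section 5.2, adds a routine source of matching text: "All IMP self-injections need to be documented in the eCRF with" a COVID-19 note in the comments log for the visit.

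**The concern.** A text match shows that a word was written, not that the pandemic caused the event. SAP 6.8.8 contains no exception for AEs, no rule for negated text, no date limit and no step at which anyone reads the matched entries. The blind review in SAP section 5 covers critical protocol deviations and major eligibility criteria.

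What is at stake is the value a subject contributes to the primary analysis. A false match replaces a zero by a positive response probability, which is larger in the arm with the higher response rate. A pandemic-caused event described in other words stays a non-response and errs the other way. For infection AEs the string decides a question that the protocol leaves open.

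**Working it through.** **1. Inputs and the plan's own figure.** Protocol 14.1: "With a significance level of 5%, a sample size of 250 subjects will provide 99% power", with EASI75 rates of 40% and 15% and pruritus rates of 30% and 15%. Protocol 14.3.16: "all significance tests will be 2-sided using the 5% significance level". Synopsis: "A total of 250 subjects will be randomised 1:1", so n = 125 per arm.

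Power = Φ{[d − 1.96·√(2·p̄(1−p̄)/n)] / √[(p₁(1−p₁) + p₂(1−p₂))/n]}

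- EASI75: d = 0.25, p̄ = 0.275. (0.25 − 1.96 × 0.0565)/0.0542 = 2.57, power 0.995. The stated 99% reproduces.
- Pruritus: d = 0.15, p̄ = 0.225. (0.15 − 1.96 × 0.0528)/0.0520 = 0.89, power 0.814. The product 0.995 × 0.814 = 0.810 agrees with the stated figure of at least 80% for both.
- Half-width of the planned 95% CI for EASI75: 1.96 × 0.0542 = 0.106, about 10.6 points.

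**2. The rule applied literally.** The strings are illustrations, not trial data.

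| Text | Match |
|---|---|
| COVID-19 infection | yes |
| not related to COVID-19 | yes |
| COVID test negative; lack of efficacy | yes |
| Coronary artery disease | yes |
| Acute coronary syndrome | yes |
| Coronavirus lockdown | yes |
| SARS-CoV-2 | no |
| pandemic travel ban | no |
| lockdown | no |
| quarantine | no |

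**3. From a match to the analysed value.**

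- A match in the discontinuation reason produces subject-onset directly.
- A match on a missed dose or visit acts indirectly. It can contribute to a prolonged interruption, or attribute rescue treatment in that window to the pandemic (protocol 14.3.1).
- A match on an assessment matters only where nothing was observed (SAP 6.8.5).
- In every case the first prior intercurrent event governs (SAP 6.8.5 and 6.8.6).

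**4. Shift in the EASI75 difference.** If a reclassified subject's imputed response probability is r, that arm's rate moves by r/125. Taking the planning rates as the MAR rates (an assumption):

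- one tralokinumab subject: 0.40/125 = +0.32 points;
- one placebo subject: 0.15/125 = 0.12 points, so −0.12 on the difference;
- k per arm: k × 0.25/125.

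The documents give no count of matches, so k is assumed.

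| k | k per arm | tralokinumab only | placebo only |
|---|---|---|---|
| 1 | +0.20 | +0.32 | −0.12 |
| 2 | +0.40 | +0.64 | −0.24 |
| 5 | +1.00 | +1.60 | −0.60 |
| 10 | +2.00 | +3.20 | −1.20 |

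Because r cannot exceed 1, no single reclassification can move an arm by more than 1/125 = 0.8 points. A pandemic dropout that the search misses shifts the difference by the same amount with the opposite sign. With equal true rates, k per arm gives k × 0/125 = 0.

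**5. Power if the matched subjects return to non-response.** Each rate is multiplied by (125 − k)/125.

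| k per arm | EASI75 | Pruritus |
|---|---|---|
| 0 | 0.995 | 0.814 |
| 5 | 0.993 | 0.794 |
| 10 | 0.989 | 0.772 |

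**The case against.** The strongest reply is that the rule does little harm and that other parts of the plan contain it. Most of this stands.

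- **Conflict with the protocol.** A reader might infer that the SAP breaks the protocol's rule for AEs. The documents do not establish that. The same protocol sentence lets infection give rise to one of the listed scenarios, and pandemic-related discontinuation is one of them. The external-circumstance rationale favours the stricter reading but does not settle it.
- **Review.** A reader might infer that nobody looks at these entries. Data queries (Appendix 3D) and a review of the planned analyses against blinded data (protocol 14.3.16) exist. Neither is tied to the matches, so the supported statement is that no check of them is documented.
- **Stray comments and self-injection notes.** A reader might infer that any COVID-19 note changes an outcome. A discontinuation needs the match in its recorded reason, and the missing-data flag needs an absent value. At a supervised on-site self-injection the rest of the visit runs per protocol (Appendix 8, section 4). This route therefore needs an attended visit, an assessment missing for an unrelated reason and no prior intercurrent event. It is possible but narrow.
- **Attribution alone decides.** It does not. An earlier non-pandemic rescue or discontinuation remains non-response.
- **Backstops.** The composite estimand counts every discontinuation, rescue use and missing value as non-response whatever the attribution, for the binary secondary endpoints too. The EASI75 Week 16 tipping-point analysis shifts the imputed values of the tralokinumab subjects concerned.

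The backstops limit the effect without correcting the classification. The composite estimand also turns genuine pandemic cases into non-response, so it cannot isolate false matches. The tipping-point analysis tests the MAR assumption, not the cause of the event, and SAP 6.6.3.1 drops it for IGA 0/1 and pruritus.

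**Conclusion.** The point holds as a gap in a stated rule. Followed literally, SAP 6.8.8 can misclassify in both directions, and it classifies infection-AE discontinuations by string while the protocol is ambiguous. No documented check would catch either.

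The expected effect is small: +0.32 or −0.12 points on the EASI75 difference per false match, and +1.0 point for five per arm, about a tenth of the CI half-width. These figures assume 125 analysed per arm, MAR response rates equal to the planning rates, and assumed counts; they ignore stratification and imputation variance. The EASI75 power calculation barely moves. Pruritus has less margin and no tipping-point analysis.

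A reader might infer that the rule manufactures a treatment effect. The arithmetic does not support this: balanced errors add nothing under the null, matches confined to placebo lower the estimate, and missed pandemic cases offset false matches. The case for change is that a stated rule can give wrong classifications and is cheap to correct.

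**What to change.** Amend SAP 6.8.8 before unblinding:

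1. Use the text search only as a screen. List every hit, together with near-misses found with wider terms such as 'SARS-CoV-2', 'lockdown', 'quarantine' and 'pandemic'.
2. Adjudicate the list blinded to treatment and record each decision in the analysis set definition document.
3. Reconcile the infection sentence in protocol 14.3.1 with the discontinuation rule in SAP 6.8.8 by stating how a discontinuation with reason 'AE', specified as COVID-19 infection, is classified in the analysis.
4. Replace `CORONA` with a term that does not match 'coronary', for example `CORONAV` plus 'corona' as a whole word.
5. After unblinding, report by arm the numbers of hits, near-misses and reclassified subjects.

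The cost is SAP wording and one short blinded listing review. No new data are needed, and the estimands and analysis models stay as they are.
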